5 LIST OF ABBREVIATIONS

| | |
|-------|--|
| ADR | Adverse Drug Reaction |
| AE | Adverse Event |
| AF | Alkaline phosphatase |
| ALT | Alanine Amine Transferase |
| AML | Acute Myeloid Leukemia |
| ANC | Absolute Neutrophil Count |
| APL | Acute Promyelocytic Leukemia |
| APTT | Activated Partial Thromboplastin Time |
| AST | Aspartate Amino Transferase |
| BM | Bone Marrow |
| CFR | Code of Federal Regulations |
| CHF | Congestive Heart Failure |
| CHMP | Committee for Medicinal Products for Human Use |
| CIMT | Association for Cancer Immunotherapy |
| CMMI | Centre for Microscopy and Molecular Imaging |
| COA | Certificate of Analysis |
| CR | Complete Remission |
| CRA | Clinical Research Associate |
| CRF | Case Report Form |
| CRO | Clinical Research Organisation |
| CTA | Clinical Trial Agreement |
| CTCAE | Common Terminology Criteria for Adverse Events |
| CTL | Cytotoxic T-lymphocyte |
| CVA | Cerebrovascular Accident |
| DC | Dendritic Cells |
| DSMB | Data Safety Monitoring Board |
| DTH | Delayed Type Hypersensitivity |
| ECG | Electrocardiogram |
| ECOG | East Cooperative Oncology Group |
| EDC | Electronic Data Capture |
| EMA | European Medical Agency |
| EOS | End Of Study |
| EOT | End Of Treatment |
| FDA | US Food and Drug Administration |
| FU | Follow Up |
| GCP | Good Clinical Practice |
| GFR | Glomerular Filtration Rate |
| GMP | Good Manufacturing Practice |

| | |
|-------|---|
| HB | Haemoglobin |
| HLA | Human Leukocyte Antigen |
| HOVON | Stichting Hemato-Oncologie voor Volwassenen Nederland |
| HSCT | Hematopoietic Stem Cell Transplantation |
| IB | Investigator Brochure |
| ICH | International Council for Harmonisation |
| ICS | Intracellular Cytokine Staining |
| IEC | Institutional Ethical Committee |
| IFN | Interferon |
| IHC | ImmunoHistoChemistry |
| IL | Interleukin |
| IMP | Investigational Medical Product |
| IMPD | Investigational Medical Product Dossier |
| IMV | Interim Monitoring Visit |
| IP | Investigational Product |
| ISO | International Organization for Standardization |
| LAA | Leukaemia Associate Antigen |
| LAP | Leukaemia Associated Phenotypes |
| LDH | Lactate DeHydrogenase |
| LN | Lymph Node |
| MDRD | Modification of Diet in Renal Disease |
| MDSC | Myeloid-Derived Suppressor Cells |
| MFC | Multicolor Flow Cytometry |
| MHC | Major Histocompatibility Complex |
| MLR | Mixed Lymphocyte Reaction |
| MRD | Minimal Residual Disease |
| N.A. | Not Applicable |
| ND | Not Done |
| NK | Natural Killer Cell |
| NO. | Number |
| NYHA | New York Heart Association |
| OMP | Orphan Medicinal Product |
| OS | Overall Survival |
| PB | Peripheral Blood |
| PBMC | Peripheral Blood Mononuclear Cell |
| PM | Project Manager |
| PSCT | Allogeneic Peripheral Stem Cell Transplantation |
| QA | Quality Assurance |
| QP | Qualified Person |

| | |
|-------|---|
| SAE | Serious Adverse Events |
| SITC | Society for Immunotherapy of Cancer |
| SOC | Standard Of Care |
| SOP | Standard Operation Procedure |
| SQV | Site Qualification Visit |
| SUSAR | Suspected Unexpected Serious Adverse Reaction |
| TAA | Tumour Associated Antigen |
| TEAE | Treatment Emergent Adverse Event |
| TMF | Trial Master File |
| TNF | Tumour Necrosis Factor |
| TTR | Time To Remission |
| VU | Vrije Universiteit / Free University |
| WBC | White Blood Cells |
| WHO | World Health Organization |
| WT | Wilms Tumour Gene |

6 SYNOPSIS

| | |
|--|---|
| Name of Sponsor/Company: DCprime bv | |
| Name of Investigational Product: DCP-001 | |
| Name of Active Ingredient: The active ingredient consists of allogeneic human dendritic cells (DCs) derived from the CD34+ progenitor AML cell line, DCOne. These DCs endogenously express several AML specific leukemia associated antigens (LAA) that include WT1, MUC1, PRAME and RHAMM. | |
| Title of Study: Allogeneic Dendritic cell Vaccination in AML oNgoing Clinical Evaluation II | |
| Short Study Title (acronym): ADVANCE II | |
| Study center(s): Approximately 3-5 sites Countries: Netherlands, Germany | |
| Coordinating Investigators: [name]. [name] | |
| Studied period (years): Recruitment time: 12 - 18 months. Treatment time: 4.5 months Follow up time: 12 months after the last patient receives the last biweekly (4 th) vaccination. Total Study duration: approximately 34 months | Phase of development: IIa, Proof of Concept |
| Rationale: Immunotherapy offers promise in AML and has created opportunities for improved outcomes. Dendritic cell (DC)-based immunotherapy has shown to be a promising strategy for the elimination of minimal residual disease (MRD) in patients with acute myeloid leukemia (AML). DCP-001 is an allogeneic dendritic cell based immunotherapeutic vaccine that expresses a number of tumour antigens that are expressed in AML and have shown clinical results when applied as peptide vaccines or loaded onto patient derived DC. Evidence for DCP-001 mediated safety, feasibility and immunological responses have been demonstrated in a Phase I study; the current study aims to generate evidence for clinical efficacy. | |
| Objectives: Primary: 
 • To assess the effect of DCP-001 on MRD. MRD will be measured by flow cytometry pre and post vaccination as a surrogate marker for established clinical endpoints in AML. • To assess the effect of DCP-001 on immune responses in AML patients in first complete remission (CR1) and persistent MRD. • To document safety and tolerability. | |

| |
|---|
| 
Secondary:
 
• To identify surrogate (immunological) markers that might correlate with clinical outcome.• To quantify any lag time between initiation of treatment & onset of effect.• To determine the effect of DCP-001 on Time to Relapse (TTR).• To determine the effect of DCP-001 on Overall Survival (OS) during the study.• To document the difference between the two vaccination regimens based on MRD outcome and immunological parameters. |
| 
Methodology:
 
International, multicentre, open-label proof of concept study without randomization and stratification. Two different dose groups are included. Group 1 consists of 10 patients that will receive 25E6 DCP-001 cells per vaccination with two additional booster vaccinations of 10E6 cells. Group 2 consists of 10 patients who will receive 50E6 DCP-001 cells per vaccination with two additional booster vaccinations of 10E6 cells.
 
Patients will be screened for eligibility for the study and evaluated at baseline, at each vaccination visit and every 8 weeks during follow up. Each patient will be followed up for 12 months after the 4th vaccination. Sera and cell samples (blood and bone marrow) will be collected when indicated for efficacy (MRD evaluation) and immune response monitoring.
 |
| 
Number of patients (planned):
 
No less than 20 patients are planned for participation
 |
| 
MRD assessment:
 
MRD will be determined at start of the vaccination, prior to the first boosting vaccination, after the last boosting and a final MRD assessment will be performed 100 days after receiving the last boost (day 224). MRD will be determined with multi-parametric flow cytometry. Flow cytometric MRD is based on leukaemia associated phenotype (LAP) that will be established at diagnosis and at specified time points post-vaccination. MRD will be reported as a percentage of the whole white blood cell compartment in complete remission, according to standardized protocols. Assessment of MRD will be performed by a central lab (VUmc).
 |
| 
Immunomonitoring:
 
○ Antigen-specific T cell mediated immunity will be measured in PBMC by ELISpot and Intracellular cytokine release against antigens known to be expressed by DCP-001 (i.e. PRAME, WT-1, MUC1, RHAMM), both pre-and at various time points post-vaccination;○ PBMC profiling will be performed both pre-and at various time points post-vaccination;○ The overall immune competence of patient's PBMC to respond to DCP-001 will be measured both pre-and at various time points;○ Biopsies will be taken from the injection site for immunohistochemistry analyses 48 hrs after the 1st vaccination and 48 hrs after the 4th vaccination. |
| 
Diagnosis and main criteria for inclusion:
 
Main Inclusion Criteria:
 
1. Confirmed diagnosis of AML according to WHO2016 criteria, including cytological, molecular and cytogenetic criteria (except acute pro-myelocytic leukaemia/APL). |

2. In CR1 (first complete remission) or CRi (incomplete blood count recovery) documented by bone marrow examination up to one month before vaccination; CR defined as less than 5% blasts in normo-cellular bone marrow, ANC $>1 \times 10^9/L$, platelet count $>100 \times 10^9/L$, no evidence of extra-medullary disease. Patients in CRi (patients with $<5\%$ blasts but with incomplete blood count recovery) should have platelets $>50 \times 10^9/L$.
3. MRD as defined by multicolour flow cytometry (MFC) at a value of $>0.1\%$, or detection of specific molecular abnormalities such as NPM1 mutation.
4. Patients that are in CR1 or CRi. Patients not having undergone consolidation therapy must have been in CR1 for at least 1 month prior to enrolment.
5. Expected and willing to undergo all study procedures, including outpatient evaluations for clinical and immunological monitoring.
6. Male or female of ≥ 18 years of age.
7. Women of childbearing potential must be using anti-conceptive therapy or use two (2) barrier contraceptive methods (one by each partner and at least one of the barrier methods must include spermicide (unless spermicide is not approved in the country or region). See section 12.8 for birth control methods deemed acceptable for this study.
8. ECOG (WHO) performance status 0-2.
9. Willing and able to provide written informed consent for participation in the study

Main Exclusion Criteria:

1. Acute Promyelocytic (APL; M3) type of AML.
2. Patients who have undergone or are scheduled for allogeneic stem cell transplantation.
3. History of previous allogeneic bone marrow or solid organ transplantation.
4. Uncontrolled or serious infections
5. Ongoing immunosuppressive therapy, other than short use of low dose steroids, i.e. equivalent to an average dose of $\leq 10\text{mg}$ of prednisone/day.
6. Chemotherapy and antineoplastic hormonal therapy within 28 days prior to the screening visits.
7. Active autoimmune disease.
8. Inadequate liver function (AST and ALT $> 3 \times \text{ULN}$, serum bilirubin $>3 \times \text{ULN}$).
9. Other active Malignancies within the last 5 years, except for adequately treated carcinoma in situ of the cervix or squamous carcinoma of the skin or adequately controlled limited basal cell skin cancer.
10. Pregnant or lactating females.
11. Major surgical procedure (including open biopsy) within 28 days prior to the first study treatment, or anticipation of the need for major surgery during the course of the study treatment.
12. Uncontrolled hypertension (systolic > 150 mm Hg and/or diastolic > 100 mm Hg) or clinically significant (i.e. active) cardiovascular disease.
13. Evidence of any other medical conditions (such as psychiatric illness, physical examination or

| |
|--|
| 
laboratory findings) that may interfere with the planned treatment, affect patient compliance or place the patient at high risk from treatment-related complications.
 
14. Known HIV, Hepatitis B and/or Hepatitis C infections.
 
15. History of hypersensitivity to the investigational medicinal product or to any excipient present in the pharmaceutical form of the investigational medicinal product.
 |
| 
Investigational product, dosage and mode of administration:
 
The investigational product is DCP-001, which consists of allogeneic human dendritic cells, expressing specific Leukaemia Associated Antigens (LAA) antigens.
 
Patients will receive either 25E6 (Group 1) or 50E6 (Group 2) DCP-001 cells/vaccination. Both groups will receive a total of 4 vaccinations at biweekly intervals (weeks 0, 2, 4 and 6) followed by 2 booster vaccinations 8 and 12 weeks after the 4th (week 6) vaccination of 10E6 cells. DCP-001 will be applied intra-dermally (2-4 injections per vaccination, 1 per booster vaccination) and is formulated as a direct injectable vaccine.
 |
| 
Duration of treatment:
 
4 vaccinations at biweekly intervals, followed by two booster vaccinations 8 and 12 weeks after the 4th (week 6) vaccination. Total treatment duration 18 weeks.
 |
| 
Reference therapy, dosage and mode of administration:
 
N.A.
 |
| 
Criteria for evaluation:
 
1. Any change in MRD (flow cytometric) as compared to baseline MRD2. Any change in immunoreactivity (specific and non-specific) as compared to baseline. |
| 
Safety endpoints:
 
1. Treatment emergent adverse events (TEAEs) will be collected in the first 48 hours after the first vaccination to determine (acute) toxicity due to intradermal injection.2. All TEAEs will be collected during the study for each patient and the grade of toxicity using Common Terminology Criteria for Adverse Events (CTCAE V4) and relationship to product determined.3. A Data Safety Monitoring Board (DSMB) will meet after every 5 patients treated to evaluate safety; written reports will be made of each meeting.4. All Serious Adverse Events (SAEs) will be reported by the investigator within 24 hours of first knowledge. All SAEs will be reported in a timely manner to the appropriate regulatory body, consistent with existing regulations. Information on relevant SAEs will be disseminated between sites in a timely manner.5. The safety and efficacy databases will include only the subjects included in study and received a least one vaccination. |

Statistical Methods:

Sample Size Assumptions: The planned sample size of 20 evaluable subjects will be distributed 1:1 with 10 subjects each in Group 1 - 25E6 DCP-001 cells per vaccination, and Group 2 - 50E6 DCP-001 cells per vaccination. Additional subjects may be enrolled to ensure that 20 evaluable subjects complete the study. The sample size is based on practical considerations, rather than strict sample size statistical considerations with a desired power for a pre-specified difference.

Statistical Analyses: Descriptive analyses of efficacy and safety variables will be used. The analysis will be performed on the data collected up to the last MRD assessment (Day 224). In general, descriptive statistics, unless otherwise noted, will include the number of subjects, mean, standard deviation, median, minimum value, and maximum value, and where applicable, 95% confidence intervals. Percentages will be calculated using the number of subjects within each treatment group. If appropriate, immune monitoring data will be summarized using the geometric mean, standard error of the geometric mean, and 95% confidence intervals of the geometric mean. Time to event variables (e.g. time to relapse or change in MRD status) will be analysed using survival analysis techniques (e.g. Kaplan-Meier estimates).

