8.2 DESCRIPTION OF THE CONDITION

Acute Myeloid Leukaemia (AML) is a disorder arising from the myeloid lineage of white blood cells, leading to accumulation of immature blasts cells in the bone marrow and peripheral blood, and disruption of normal haematopoiesis. The disease is heterogeneous with respect to morphology, immune-phenotype, cytogenetic and molecular genetics, clinical characteristics and outcome.

AML is relatively rare, afflicting annually 3–5 cases per 100,000 persons but remains the most common form of acute leukaemia among adults. As also the deadliest form, it accounts for the largest number of annual deaths in the United States and Europe. With a median age at diagnosis of 67 years, this disease is far more common in the elderly (1). In this age group, AML has a particularly dismal outcome with less than 10% of the patients being alive 5 years after the diagnosis, as compared to 40% in the young (1,5). With an age dependent rise in incidence and a peak at ~22 cases per 100,000 in the geriatric population, AML has a devastating impact on the survival of this age group.

The conventional initial treatment of AML is intensive chemotherapy followed by an autologous/allogeneic hematopoietic stem cell transplantation (HSCT). Due to co-morbidity in the elderly patients, some cannot tolerate aggressive chemotherapy and, in patients ineligible for induction chemotherapy, current treatment options are focused mainly on supportive measures, such as red blood and platelet transfusions when needed and antibiotics for infections. Even when induction chemotherapy is able to induce complete remission, relapse rates remain high (60-80%) due to the

presence and outgrowth of residual AML cells in bone marrow (BM); so called minimal residual disease (MRD), which directly relates to the poor survival rates.

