8.10.4 BLOOD, BONE MARROW AND SKIN BIOPSY SAMPLING

This study involves frequent blood and bone marrow sampling. The total number and volume of blood samples is detailed in Table 4.

For immunomonitoring purposes, 70 mL of blood will be collected in heparin coated tubes. Samples will be taken at screening, start vaccination (d=0), day 44, day 77, day 128, day 140 and day 224.

For hematology diagnostic purposes, 21 mL of blood will be collected in heparin coated tubes.

Bone marrow aspirates (at least 3 ml or 16.106 cells for LAP analysis and 10 ml for biobanking) will be collected in heparin coated tubes. Samples will be taken at baseline (d=0), day 98, day 140, and at day 224. All BM samples should be obtained preferably from the first tap, gathered in heparin-coated tubes and kept at room temperature. In any case it should be indicated whether the sample is from the first or second tap. In addition, a single skin biopsy will be taken at 48h post 1st vaccination, 4th vaccination and 2nd booster vaccination. The biopsy will be 4-6 mm and will be taken using a standard punch needle. The injection site to be biopsied will be chosen at random and an injection site will be used for biopsy only once (no repeat biopsy of any injection site).

Table 4: Invasive procedures and sample sizes

| Visit no. | 1 | 2 | 3 | 4 | 5 | 6 | 7 | 8 | 9 | 10 | 11 | 12 | 13 |
|---|----|-----|----|-----|-----|-----|----|----|-----|-----|-----|-----|-----|
| Day | | 0 | 2 | 14 | 28 | 42 | 44 | 77 | 98 | 126 | 128 | 140 | 224 |
| quantity of Blood (mL) | | | | | | | | | | | | | |
| For diagnosis | 21 | 21 | | 21 | 21 | 21 | | | 21 | 21 | | 21 | 21 |
| For HLA classification | 24 | | | | | | | | | | | | |
| For immunomonitoring | | 70 | 70 | | | | 70 | 70 | | | 70 | 70 | 70 |
| quantity of Bone Marrow aspirate (mL) | | | | | | | | | | | | | |
| for diagnosis | | > 3 | | | | | | | > 3 | | | > 3 | > 3 |
| For biobank | | 10 | | | | | | | 10 | | | 10 | 10 |
| Vaccination | | | | | | | | | | | | | |
| number of intradermal injections ¹ | | 2-4 | | 2-4 | 2-4 | 2-4 | | | 1 | 1 | | | |
| Skin test | | | | | | | | | | | | | |
| number of biopsies ² | | | 1 | | | | 1 | | | | 1 | | |

1) Depending on dose: 2 for low dose, 4 for high dose and 1 for boosting dose

2) 1 biopsy to be taken from 1 injection site

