9.1.3 Exploratory Objectives

1. To document the number and duration of subsequent remissions.
2. To identify subgroups of patients most likely to benefit from treatment.

Immune monitoring:

Monitoring the immune response is an essential element to evaluate efficacy. The analysis of the immune response against tumour antigens in blood samples from these patients pre and post vaccination allows a better understanding of

1. the underlying mechanisms of action of the immunotherapy;
2. the prognostic value of immunological parameters; and
3. the use of new knowledge about immune parameters to design improved immunotherapy treatments for the future.

The following activities will be performed:

1. Antigen-specific T cell mediated immunity will be measured in PBMC by IFN- α ELISpot and intracellular cytokine release against antigens present in leukemic blasts and also known to be expressed by DCP-001 (i.e. PRAME, WT-1, MUC1, RHAMM). Both pre-and various time points post-vaccination will be analysed.
2. Changes in profiles of different PBMC populations. This includes T-cell profiles, regulatory T cells, MDSC, NK cells etc., according to the same schedule as for antigen-specific responses.
3. General T-cell activation capability and thus immune competence of patients will be analysed by measuring T-cell proliferation and cytokine release following stimulation with DCP-001 in vitro. Pre- and post-vaccination samples will be compared.

4. Biopsies will be taken from the injection site and analysed for specified markers in order to identify the local immune infiltration process.

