12.5 END OF TREATMENT

Study discontinuation refers to complete withdrawal from the study treatment. The reason for discontinuation from treatment must be recorded. Study discontinuation can be based on one or more of the following criteria:

- Adverse event(s) (physician's discretion)
- Disease progression
- Protocol violation
- Subject withdrew consent
- Lost to follow-up
- Administrative problems
- Death
- Treatment duration completed as per protocol

Furthermore, treatment ends when:

1. No return to baseline or no return to grade 1 non-hematological toxicity at any time during/after the vaccination.
2. Related SAE not otherwise categorized within the CTC v4.0 criteria (see Appendix B) but defined as severe or life threatening at any time during/after vaccination.

Based on the above, there is a differentiation between treatment withdrawal (withdraw treatment, but continue follow-up) and study drop-out (withdrawal from study e.g. unwillingness of the patient to comply with study procedures, withdraw consent, or lost to follow-up).

DCPrime must be notified and the reason(s) for treatment withdrawal/study drop-out should be documented in the eCRF; all follow-up data should also be reported.

Patients who have received at least one dose of DCP-001 who are withdrawn, or withdraw from the study will be treated according to protocol as EOT and EOT pages will be completed. If the patient does not withdraw informed consent, he/she will be requested to enter the follow up phase of the study. These patients will follow the normal schedule of the study excluding the injection of study treatment and the procedures at these visits will occur at the investigators' discretion. These patients will continue to be followed up until EOS or EOT of last patient who completed the study, whichever comes first

If the patients who are required to enter follow up do not enter follow up, for any reason, they must be requested to complete an EOT and EOS visit.

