16.2 STATISTICAL AND ANALYTICAL PLANS

No inferential analysis is planned for the study; only descriptive analyses will be used. In general, descriptive statistics, unless otherwise noted, will include the number of subjects, mean, standard deviation, median, minimum value, and maximum value, and where applicable, 95% confidence intervals. Percentages will be calculated using the number of evaluable subjects within each treatment group. If appropriate, immune monitoring data will be summarized using the geometric mean, standard error of the geometric mean, and 95% confidence intervals of the geometric mean. Unless otherwise stated, all summary tables will present descriptive statistics and/or frequency by visit for each treatment group. The analysis will be performed on the data collected up to the last MRD assessment (Day 224).

All statistical analyses and data summaries will be completed using SAS Software (version 9.2 or greater).

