16.2.3 Analysis of Efficacy Variables

MRD levels and immune responses will be summarized descriptively by treatment group and visit as described above. Time to event variables (e.g. time to relapse) will be analysed using survival analysis techniques (e.g, Kaplan-Meier estimates).

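### Kaplan-Meier is the example method for time to change in MRD status, with no rule for relapse or death; if both are censored, it overstates MRD conversion by an amount that depends on the relapse rate

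*Protocol*

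**What the plan says.** The synopsis, under Statistical Analyses, states: "Time to event variables (e.g. time to relapse or change in MRD status) will be analysed using survival analysis techniques (e.g. Kaplan-Meier estimates". Section 16.2.3 has almost the same sentence but leaves MRD status out: "Time to event variables (e.g. time to relapse) will be analysed using survival analysis techniques (e.g, Kaplan-Meier estimates". Kaplan-Meier is the only technique named in either place, and in both it is an example. Neither place defines the event, gives its direction, states a censoring rule, or mentions competing events or cumulative incidence.

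The surrounding text matters as well:

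- The synopsis lists as a criterion for evaluation: "Any change in MRD (flow cytometric) as compared to baseline MRD".
- Marrow sampling (section 8.10.4): "Samples will be taken at baseline (d=0), day 98, day 140, and at day 224".
- Analysis cut-off (section 16.2): "The analysis will be performed on the data collected up to the last MRD assessment (Day 224".
- Section 12.5 lists disease progression among the reasons for discontinuation. For patients who stop treatment but stay in the study it says: "These patients will follow the normal schedule of the study excluding the injection of study treatment". The procedures at those visits are left to the investigator.
- Section 14.1 runs the follow-up visits to the end of study or to disease progression.
- Section 8.2 gives the only relapse figure: "relapse rates remain high (60-80" per cent, with no time attached.

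**The concern.** Entry requires MRD (inclusion criterion 3). For a patient who is MRD-positive at entry, the favourable change in status is to become negative while in remission. A patient who dies cannot do this, and a patient who relapses is no longer in the remission in which the conversion was to be seen. Kaplan-Meier for a single event type has only one ordinary place for such patients: they are censored and treated as if they would go on to convert at the same rate as those still in remission. One minus the curve then describes a setting in which nobody relapses or dies.

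The resulting error has one direction. It is zero without competing events and grows with them. MRD is a primary endpoint, the study has no control group in which the same error would appear, and section 8.8 intends the results to inform a Phase IIb design. The matter is separate from the spacing of the marrow samples and would remain if every conversion date were known exactly.

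Time to relapse has the same structure, with death in remission as the competing event.

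**Working it through.** **The plan's own figure.** Section 16.1 gives one calculated figure: 20 subjects detect a 22-point difference from 90% with MRD (two-tailed one-sample z-test, 80% power, 5% level). With p0 = 0.90 and p1 = 0.68:

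n = (1.960·√(0.90·0.10) + 0.842·√(0.68·0.32))² / 0.22² = (0.588 + 0.393)² / 0.0484 ≈ 19.87, so 20.

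It reproduces. It concerns a proportion, not a time-to-event curve, and is used below only as a source for an illustrative 22%.

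**Inputs.**

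- MRD assessments after baseline at Days 98, 140 and 224 (section 8.10.4).
- Assumed: true cumulative incidence of conversion by Day 224 of 22%. The Protocol gives no conversion rate.
- Assumed: probability r of relapse or death by Day 224, apart from conversion, of 10-60% at constant hazard. The Protocol gives no Day-224 rate.
- Assumed: the same conversion probability h at each of the three visits among patients still at risk.

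**Formulas.** The proportion free of relapse and death at day t is S(t) = (1 − r)^(t/224).

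- Cumulative incidence = h·S(98) + h(1 − h)·S(140) + h(1 − h)²·S(224), solved for h so that it equals 0.22.
- One minus Kaplan-Meier with relapse and death censored = 1 − (1 − h)³.

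**Worked row, r = 30%.** S = 0.8555, 0.8002, 0.7000. The solution is h = 0.1030: 0.0881 + 0.0739 + 0.0580 = 0.2200. Kaplan-Meier returns 1 − 0.8970³ = 27.8%, which is 5.8 points too high.

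| Relapse or death by Day 224 (assumed) | True conversion | 1 − Kaplan-Meier | Excess (points) |
|---|---|---|---|
| 0% | 22% | 22.0% | 0 |
| 10% | 22% | 23.6% | +1.6 |
| 20% | 22% | 25.5% | +3.5 |
| 30% | 22% | 27.8% | +5.8 |
| 40% | 22% | 30.7% | +8.7 |
| 50% | 22% | 34.4% | +12.4 |
| 60% | 22% | 39.3% | +17.3 |

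For scale, the standard error of a 22% proportion is √(0.22·0.78/20) = 9.3 points for all 20 patients and 13.1 for a group of 10.

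**Which row applies?** Day 224 is about 7.4 months. If a relapse rate p of 60-80% is reached at H months with constant hazard, the Day-224 rate is 1 − (1 − p)^(7.4/H).

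| Horizon for 60-80% (assumed) | Relapse by Day 224 | Excess at 22% conversion (points) |
|---|---|---|
| 12 months | 43-63% | +9.7 to +19.0 |
| 24 months | 25-39% | +4.5 to +8.4 |
| 36 months | 17-28% | +2.9 to +5.3 |
| 60 months | 11-18% | +1.7 to +3.1 |

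**Sensitivity to the conversion rate.** Over r = 20-60%, the excess is +1.6 to +8.2 points at 10% conversion and +6.2 to +29.1 at 40%. Section 16.1's 22 is a difference from 90%, so 68% would have MRD and 32% would not. At 32% conversion the excess is +5.0 to +24.3.

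**Check with whole patients.** Take 20 patients with 1, 2 and 3 conversions at Days 98, 140 and 224, so 6/20 = 30% convert. With 2, 1 and 1 competing events before those visits, 18, 16 and 13 are at risk, and 1 − (17/18)(14/16)(10/13) = 36.4%, or +6.4 points. With 4, 2 and 2 competing events, 16, 13 and 9 are at risk, and 1 − (15/16)(11/13)(6/9) = 47.1%, or +17.1 points.

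**Time to relapse.** Assume a cumulative incidence of relapse of 60%, death in remission of 5, 10 or 15%, and constant cause-specific hazards. With d the proportion dying in remission, 1 − Kaplan-Meier = 1 − (1 − 0.60 − d)^(0.60/(0.60 + d)). This gives 62.1, 64.4 and 67.0%, or +2.1, +4.4 and +7.0 points.

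**The case against.** The strongest reply is that the Protocol does not say what the calculation assumes, and several parts of that reply stand.

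- A reader might infer that the plan prescribes censoring of relapse and death. It does not. Kaplan-Meier is an example, cumulative incidence is itself a survival technique, and section 16.2.4 leaves full details to the SAP. What remains is that the one method named, applied in the ordinary way, gives the wrong quantity for the most natural reading of the event.
- A reader might infer that relapse makes conversion impossible. Only death does so strictly. Patients off treatment keep the visit schedule, and section 9.1.3 has the exploratory objective "To document the number and duration of subsequent remissions". Under the synopsis criterion of any change, a rise in MRD or a relapse could even count as an event. The supportable statement is that conversion within the current remission is no longer possible. If relapse did count as a change, one curve would mix benefit with failure, which is a further reason to define the event.
- A reader might infer that the primary MRD analysis is biased. Section 16.2.3 summarises MRD levels descriptively by group and visit, and this problem does not touch those summaries. MRD status as a time-to-event variable appears only in the synopsis.
- No inferential analysis is planned and each group has about 10 patients, so random error is large beside the smaller values in the table. This limits the consequence, but it does not make a one-directional error acceptable when a direct estimate is available from the same data.

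**Conclusion.** The point holds in conditional form. If time to change in MRD status means time to conversion to MRD-negative, and relapse and death are censored, one minus Kaplan-Meier is never below the true probability of conversion in remission, and it is above it whenever conversions follow competing events. The direction follows from the method; the size does not follow from the Protocol. At an assumed 22% conversion it runs from +1.6 points with 10% relapse or death by Day 224 to +17.3 points with 60%.

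A reader might take the 30-60% rows and quote 6 to 17 points as the inflation. The documents do not support a single range: they give no conversion rate, and the 60-80% relapse has no horizon. If relapse is slow (60-80% reached only at 60 months), the excess is about 2 to 3 points; if it is reached within 12 months, about 10 to 19. Nor can relapse be called more common than conversion by Day 224, since neither rate is given for that day.

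The correction is worth making because it is cheap and the error favours the product. Time to relapse is a smaller issue.

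**What to change.** In the synopsis and section 16.2.3:

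1. Define the event as conversion from MRD-positive to MRD-negative in remission. Inclusion criterion 3 also admits patients on a molecular abnormality, so say how a patient without flow-cytometric MRD at baseline is counted.
2. Estimate it by the cumulative incidence function (Aalen-Johansen), with relapse and death as competing events.
3. For time to relapse, use cumulative incidence with death in remission as the competing event, and show relapse-free survival (relapse or death) by Kaplan-Meier beside it.
4. Keep Kaplan-Meier for overall survival.

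How new anti-leukaemic therapy or transplant is handled is an estimand choice that can stay with the SAP.

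The cost is a few sentences in two places and a standard option in the software; no new data or visits are needed. The reported conversion figure becomes somewhat less favourable.
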